### Vitals

Analysis Visit	Target Day	Study Day Window
----------------	------------	------------------

Week 1, Day 2	2	2
Week 1, Day 3	3	3
Week 1, Day 4	4	4-6
Week 1, Day 8	8	7-9
Week 1, Day 11	11	10-12
Week n, Day 7*n+1  (n = 2, 3, 4, 5, 6, 7, 8, 9, 10, 11, 12, 13, 14)	7n+1	Target day -2, Target day +4
Week 15, Day 106	106	104, Day 113-3
Week 16, Day 113 Pre-dose	113	Day 113-2, Day 113
Week 16, Day 114	114	Day 113 + 1
Week 16, Day 115	115	Day 113 + 2
Week 16, Day 116	116	Day 113 + 3
Week 17, Day 120	120	Day 113 + 4, 124
Week 18, Day 127	127	125-131
Week 20, Day 141	141	132-148
Week n, Day 7*n+1  (n = 22, 24, 26,.. to 258 in increments of 2)	7n+1	Target day -6, Target day +7
Week 260, Day 1821	1821	>1814

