2.2 Schedule of Activities

Table 2-1. Phase 1b Schedule of Activities – Screening Through Week 5

	Screening	Baseline	Treatment Period ^a Visits for Weekly and Biweekly dosing																		5	PD Visit	SFU/EOS ^b		
			Study Week		Study Day		Hours post dose		1	2	3	4	8	11	15	22	29	30	31	32	36				
			Pre-dose	0	0.25	0.5	1	2	6	12	24	48	72			Pre-dose	0	6	12	24	48	72			
GENERAL AND SAFETY ASSESSMENTS																									
Informed Consent	X																								
Demographics	X																								
Medical History	X																								
GVHD/Transplant History	X																								
Physical Examination	X																							X	
Vital Signs	X	X	X	X	X	X	X	X	X	X	X	X	X	X	X	X	X	X	X	X	X	X	X		
Height	X																								
Weight	X	X																							
ECG ^c	X	X																						X	
Chest X-ray ^d	X																								
cGVHD DISEASE ASSESSMENTS																									
NIH cGVHD Response Assessment (NIH Form A) ^f			X																					X	
GVHD Staging ^g	X																								
Pulmonary Function Test ^g			X ^h																					X	

Page 1 of 3

Footnotes defined on last page of table

Table 2-1. Phase 1b Schedule of Activities – Screening Through Week 5

Study Week	Screening	Baseline	Treatment Period ^a Visits for Weekly and Biweekly dosing																		5	PD Visit	SFU/EOS ^b
			1	2	3	4	8	11	15	22	29	30	31	32	36	Anytime							
Study Day	-28	-1	Pre-dose	0	0.25	0.5	1	2	6	12	24	48	72	Pre-dose	0	6	12	24	48	72			
Hours post dose																							
CLINICAL OUTCOME ASSESSMENTS																							
LABORATORY ASSESSMENTS																							
Clinical Chemistry and Hematology	X	X						X		X		X	X	X							X	X	X
Urinalysis	X																						
Pregnancy Test ^j	X	X												X									
Coagulation (PT, INR, and aPTT)	X																						
FSH Test (postmenopausal only) ^k	X																						
HIV, Hepatitis B & C	X																						
Drug and Alcohol Screen	X																						
Tuberculosis Testing ^l	X																						
Lymphocyte Subsets ^m			X					X		X	X	X	X	X				X	X	X			
Biomarker Development Sample ^m			X					X		X	X		X	X	X								
Pharmacogenetic sample ^{m,n}			X																				
PBMC ^m			X							X				X									
PHARMACOKINETIC AND ANTIBODY ASSESSMENTS																							

Page 2 of 3

Footnotes defined on last page of table

Table 2-1. Phase 1b Schedule of Activities – Screening Through Week 5

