3.2.2.1 Toxicology

In the 1- and 3-month repeat-dose toxicology studies in the cynomolgus monkey (dose levels up to 300 and 100 μ g/kg, respectively, weekly subcutaneous [SC] injection), the no observed adverse effect level (NOAEL) dose was 30 μ g/kg based on the observation of increased heart rate with attenuated diurnal rhythm at 100 μ g/kg or greater. In addition, reversible decreases in red blood cell (RBC) mass, platelet and neutrophil counts were observed at 300 μ g/kg in the 1-month study. In the rat single-dose safety pharmacology study evaluating respiratory function (dose levels: 100, 500, and 2000 μ g/kg, single SC injection), audible respiration, decreased tidal volume and

increased respiration rate were observed at 2000 µg/kg. The heart rate, hematologic and respiratory changes were reversible, and are considered clinically monitorable.

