## Appendix G. Analytical Windows

The last visit with non-missing assessment prior to first dose will be defined as a baseline visit (unless specified otherwise) and the analysis visit name will be “Baseline”. For any visit up to Day 1 pre-dose which is not a baseline visit, the analysis visit will be ‘Pre-Analysis’. For Day 1 post-dose visits, and safety follow-up visit, the analysis visit will be same as the scheduled visit. For any unscheduled visit post safety follow-up visit, the analysis visit will be considered as safety follow-up visit. For post-dose assessments on Day 29 (the day corresponding to Week 4 dosing) and Day 113 (the day corresponding to week 16 dosing), the analysis visit will be same as the scheduled visit. Remaining visits (scheduled visit, unscheduled visit, progressive disease visit, or end of treatment visit) after Day 1 for any assessment will be mapped to the analysis visit based on visit windows defined in the tables below for that assessment. Only visits applicable for that assessment and phase of the study as per the Schedule of Activities tables in the study protocol will be considered for analysis.

Data collected through central lab and local lab will both be mapped into analysis visit windows. The local lab data can only be used in analysis when there is no central lab data available in the analysis visit window.

If more than one visit with non-missing data falls within an analysis visit window, the visit closest to the target day will be considered for analysis. If two visits are equidistant from the target day, the latest visit (or time if on the same day) will be considered. If more than one evaluation has same date and time (for chemistry, hematology or pharmacodynamics results), the value with the smallest accession number will be considered.

Analysis visit windows for selected assessments are included in tables below. For remaining assessments, no visit window will be applied. Day 29 and Day 113 used in Study day window calculation in the tables below is the respective study day when Week 4 dose and Week 16 dose was received. If that dose is missing, then 29 and 113 is used for respective calculation.

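### SAP Appendix G gives vital signs no windows for Days 30, 31 and 32, so 24, 48 and 72 h readings after the Week 4 dose drop out of the by-visit summaries

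*SAP*

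**What the plan says.** **Windows.** The vitals table in SAP Appendix G gives separate rows to Days 2, 3 and 4 after the first dose. It then uses one generic line for weeks "n = 2, 3, 4, 5, 6, 7, 8, 9, 10, 11, 12, 13, 14", with target day 7n+1 and window "Target day -2, Target day +4". After the Week 16 dose it again has separate rows, starting at "Week 16, Day 114" and continuing to Day 116, each counted from the actual dose day. There are no rows for Days 30, 31 or 32.

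**Selection.** When several visits with data fall in one window, "the visit closest to the target day will be considered for analysis". Ties go to the latest.

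**Exception.** "For post-dose assessments on Day 29 (the day corresponding to Week 4 dosing) and Day 113", the analysis visit stays as scheduled. The other visits after Day 1 (apart from the safety follow-up) "will be mapped to the analysis visit based on visit windows defined in the tables below for that assessment".

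**Planned summaries.** SAP section 9.1 plans summaries at all scheduled time points unless specified otherwise. Section 9.6.4 plans values and changes from baseline at all time points for blood pressure, heart rate and temperature, plus post-baseline maximum and minimum.

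**Schedule.** Protocol section 2.2, "Table 2-1. Phase 1b Schedule of Activities – Screening Through Week 5", has columns for study days 29, 30, 31, 32 and 36, with post-dose hours running to 24, 48 and 72 after the Week 4 dose. Protocol section 9.1.2 allows visits to move by 1 day either way through Week 4.

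**The concern.** Table 2-1 sets out two serial post-dose profiles, one after the first dose and one after the Week 4 dose. The vitals windows preserve the first and collapse the second into a single value. The pharmacodynamic table in the same appendix has its own rows for Day 30 and Day 32, and the vitals table itself splits out the days after the Week 16 dose. The gap at Week 4 therefore looks like an omission rather than a choice.

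Safety is the primary endpoint, and SAP section 9.6.1 includes vital signs in its analysis. Heart rate has particular interest here: the monkey no-adverse-effect level was set on "the observation of increased heart rate with attenuated diurnal rhythm" at higher doses (Protocol section 3.2.2.1), and the predicted Cmax margin at the highest planned dose is 1.3-fold (Protocol section 3.2.2.2). By Week 4 a subject is at the fifth weekly dose (Days 1, 8, 15, 22, 29) or the third biweekly dose (Days 1, 15, 29). The readings over the next three days are thus a repeat-dose profile. As written, the by-visit tables would not show it.

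A second effect is mislabelling. The generic line is centred on nominal Day 29, so a one-day shift in dosing can put a post-dose reading in the row that normally holds a pre-dose one.

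**Working it through.** The plan states no figure to reproduce. The check enumerates the windows and applies the selection rule.

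**Step 1: windows from the generic line** (target = 7n+1; window = target-2 to target+4).

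| n | Target day | Window |
|---|---|---|
| 3 | 7×3+1 = 22 | 20 to 26 |
| 4 | 7×4+1 = 29 | 27 to 33 |
| 5 | 7×5+1 = 36 | 34 to 40 |

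Days 30, 31 and 32 fall only in the Week 4 window.

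**Step 2: which reading is kept** (smallest distance to Day 29; ties to the latest). The allowed shift of 1 day gives dose days 28, 29 and 30.

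| Week 4 dose | Pre-dose (distance) | 24 h | 48 h | 72 h | Kept as Week 4, Day 29 |
|---|---|---|---|---|---|
| Day 28 | Day 28 (1) | Day 29 (0) | Day 30 (1) | Day 31 (2) | 24 h |
| Day 29 | Day 29 (0) | Day 30 (1) | Day 31 (2) | Day 32 (3) | pre-dose |
| Day 30 | Day 30 (1) | Day 31 (2) | Day 32 (3) | Day 33 (4) | pre-dose |
| Dosing-day reading absent | – | Day 30 (1) | Day 31 (2) | Day 32 (3) | 24 h |

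In every row, the 24, 48 and 72 h readings get no analysis visit of their own. In two rows a 24 h reading is reported as the Week 4 value.

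**Step 3: does the exception rescue them?** It covers readings on the dosing day itself, so the 6 and 12 h readings keep their visit. If it also reached the following days, the vitals rows for Days 114 to 116 and the pharmacodynamic rows for Days 30 and 32 would not be needed.

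**Step 4: nominal or actual Day 29?** Appendix G says that Day 29, where used in a window calculation, means the actual dose day. The generic vitals line uses a target of 7n+1 instead. If it were nevertheless re-centred on the dose day, the Day 28 mislabelling would disappear. The pre-dose reading would then sit at distance 0 and the later ones at 1, 2 and 3, so all three would still be dropped.

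**Step 5: are vital signs scheduled on those days?** Table 2-1 has about 27 columns: screening and baseline (2), first-dose hours (11), Days 8, 11, 15 and 22 (4), Week 4 hours (7), Day 36 (1), progressive disease and follow-up (2). The vital-signs row has 23 marks. If Days 30, 31 and 32 were all blank, 23 of the remaining 27-3 = 24 columns would need a mark, including at least one of the two hour-0 dosing columns. That is implausible but not impossible.

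**The case against.** **The schedule text is damaged.** The columns for Days 30 to 32 are visible, but the marks are not aligned to them, and those columns could exist for blood sampling. Counts of marks in these tables are not fully reliable: the biweekly dosing row of Table 2-1 shows two, where three doses fall by Week 4. This stands as a reason to check the source table first. It does not overturn the point, since the count in Step 5 leaves little room for all three days to be blank.

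**The values are not lost.** Section 9.6.4 also plans post-baseline maximum and minimum by dose level, SAP section 7.1 plans subject-level listings and plots of vitals for dose level review meetings, and section 9.6.2 names tachyarrhythmias among possible events of interest. This stands, and it limits the consequence to timing. A reader might infer that a heart-rate signal would go unseen; the documents do not support that. Nor do they give a time course for the monkey finding, so a peak one to three days after a dose is conjecture.

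**The Week 16 rows.** Table 2-2 as shown has Day 113 and then Day 120, so a reader might infer that the rows for Days 114 to 116 are empty and should go, or that Week 4 is the only repeat-dose profile. Neither follows. Table 2-2 is partly redacted, and the Appendix G text, the vitals rows and the pharmacodynamic rows all treat Week 16 as a serial profile.

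**The qualifier in section 9.1.** Appendix G could be read as specifying otherwise. However, section 9.6.4 carries no such qualifier, and nothing in Appendix G presents the omission as intended.

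**Conclusion.** The gap is real on the SAP's text. The Week 4 vitals window runs from Day 27 to Day 33, keeps one visit, and leaves the 24, 48 and 72 h readings out of the by-visit summaries that section 9.6.4 plans. A Day 28 dose also lets a 24 h post-dose reading appear as Week 4, Day 29.

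The size is up to three timed sets of vital signs per subject who attends those visits. Multiplying by the roughly 30 planned escalation subjects gives 3×30 = 90, and a reader might take that as the loss. It rests on planned enrolment. The SAP reports that enrolment to cohort 5 at its planned dose was discontinued and that the study was terminated early, so the number depends on the subjects actually treated. It is also too strong to say that the Day 29 pre-dose value always wins, as Step 2 shows.

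The conclusion assumes that vital signs are marked on Days 30 to 32 in the source Table 2-1. The limit on the harm assumes that maximum/minimum summaries use all post-baseline records, which section 9.6.4 does not restrict. The analysis is descriptive and no hypothesis test is affected. The change is still worth making because the profile belongs to the primary safety analysis and restoring it needs only data already scheduled.

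**What to change.** First confirm in the source Table 2-1 that vital signs are marked on Days 30, 31 and 32. If so, replace the generic vitals lines for Weeks 3 to 5 with the SAP's own Week 16 pattern, where Day 29 is the actual Week 4 dose day as Appendix G already defines it:

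| Analysis visit | Window | Dose on Day 28 | Day 29 | Day 30 |
|---|---|---|---|---|
| Week 3, Day 22 | 20 to Day 29-3 | 20–25 | 20–26 | 20–27 |
| Week 4, Day 29 pre-dose | Day 29-2 to Day 29 | 26–28 | 27–29 | 28–30 |
| Week 4, Day 30 | Day 29+1 | 29 | 30 | 31 |
| Week 4, Day 31 | Day 29+2 | 30 | 31 | 32 |
| Week 4, Day 32 | Day 29+3 | 31 | 32 | 33 |
| Week 5, Day 36 | Day 29+4 to 40 | 32–40 | 33–40 | 34–40 |

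Each case covers Days 20 to 40 without gap or overlap, and meets the unchanged Week 2 (13 to 19) and Week 6 (from 41) windows. Keep the Day 114 to 116 rows, and reconcile them with the unredacted Table 2-2. The cost is a few lines in one appendix table and the matching programming. No new data are needed.

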CRF = case report form; cGVHD = chronic graft versus host disease; ECG = electrocardiogram; EOS = end of study for individual subject; EOT = end of therapy; GVHD = graft versus host disease; NIH = National Institutes of Health; PBMC = peripheral blood mononuclear cell; PD = progressive disease; PFT = pulmonary function test; PK = pharmacokinetics; Q2W = every 2 weeks; SFU = safety follow-up

^a Subjects who withdraw early from treatment will complete the EOT visit and Safety follow-up visit **within a window of \pm 7 days of the next regularly scheduled visit after the last dose of efavaleukin alfa, consisting of all assessments included in the week 52 visit.**

^b Safety follow-up visit will be done 6 weeks (\pm 3 days) after the last dose of efavaleukin alfa. Women of childbearing potential will be required to complete a pregnancy test at this visit.

^c At the discretion of the Sponsor, following discussion and agreement between the principal investigator and medical monitor, subjects responding to efavaleukin alfa (as assessed by the end of week 50), who wish to continue treatment, will complete week 52 assessments and may continue to receive efavaleukin alfa treatment at their current dosing regimen for up to an additional 52 weeks (see [Table 2-3](#)). The remaining subjects will complete the week 52/EOT visit and 6-weeks of safety follow-up after the last dose of efavaleukin alfa.

^d A single ECG will be collected prior to blood draws or other invasive procedures. See Section [9.2.3.3](#).

^e Record steroid use and/or changes to dose on concomitant medication CRF page.

^f A 2 or 6 minute walk test is optional for the NIH Form A assessment.

^g For subjects on biweekly dosing arm, beginning at week 18, subjects come in for biweekly visits.

^h PFTs (spirometry) will be used in the NIH Form A assessment unless the subject is unable to comply. PFTs must be obtained at the Baseline visit unless they were performed at the Screening visit. Thereafter PFTs are strongly preferred at all visits which include the NIH Form A assessment and must be performed for all subjects who have an abnormal PFT at Baseline, who have known pulmonary GVHD or who have new pulmonary symptoms. If PFTs cannot be performed as part of the NIH Form A assessment, the lung symptom score should be substituted.

For women of childbearing potential, on study pregnancy tests are urine.

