9.1.2 Treatment Period

Visits will occur per the Schedule of Activities (see [Table 2-1](#), [Table 2-2](#), [Table 2-3](#), [Table 2-4](#), [Table 2-5](#), [Table 2-6](#), [Table 2-7](#), and [Table 2-8](#)). In the phase 1b part of the study, visits may be completed within a visit window of \pm 1 day through the week 4 visit. After the week 4 visit, the visit window may increase to \pm 3 days from the scheduled visit date for those phase 1b subjects on Q2W dosing and \pm 2 days from the scheduled dose date for those subjects on QW dosing.

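### SAP Appendix G's weekly windows open 2 days before target, so a compliant Q2W non-dosing visit 3 days early is assigned to the previous week

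*SAP*

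**What the plan says.** Protocol 9.1.2 allows 1 day either side through week 4. Then "After the week 4 visit, the visit window may increase to" plus or minus "3 days from the scheduled visit date for those phase 1b subjects on Q2W dosing", and plus or minus "2 days from the scheduled dose date for those subjects on QW dosing". The Table 2-2 footnote on visit frequency reads "For subjects on biweekly dosing arm, beginning at week 18, subjects come in for biweekly visits", so until then Q2W subjects attend every week, dosing or not.

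SAP Appendix G has one set of windows for both regimens. Vitals weeks 2-14, chemistry/hematology weeks 2-7 and pharmacodynamic (PD) weeks 6-11 all use "Target day -2, Target day +4". The nominal visit label is kept only for Day 1 post-dose visits, post-dose assessments on the week 4 and week 16 dosing days, and safety follow-up. Otherwise, "Remaining visits (scheduled visit, unscheduled visit, progressive disease visit, or end of treatment visit) after Day 1 for any assessment will be mapped" by study day. When several visits share a window, "the visit closest to the target day will be considered for analysis".

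Two other tolerances matter. Table 2-2 holds doses to 1 day either side (2 days once a redacted dose is selected). Table 2-1 holds PD and related blood samples on non-dosing days to 12 hours either side through week 5.

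**The concern.** The SAP window fits the 2-day QW tolerance but not the 3-day Q2W tolerance. A site can follow the visit schedule exactly and still have a value removed from the by-week tables, in the Q2W cohorts only. By-visit laboratory and vital-sign summaries are part of the primary safety analysis (SAP 9.6.1, 9.6.3.1, 9.6.4). Each cohort is planned at 3 to 6 DLT-evaluable subjects, so one lost value can visibly move a weekly mean. QW and Q2W profiles would also not be handled alike.

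SAP 9.7.1.2 hints at the cause. It takes more than 9 days (QW) and more than 16 days (Q2W) after the last dose as outside the protocol window, that is 7 + 2 and 14 + 2. With the 3-day visit tolerance, Q2W would be 14 + 3 = 17. The SAP may have carried 2 days over to both regimens. This is suggestive only.

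**Working it through.** **Inputs.** The target day for week n is 7n + 1, and the weekly row is 7n - 1 to 7n + 5 (SAP Appendix G). The rows listed singly open at the same point: chemistry week 8 at Day 55 (57 - 2) and vitals week 15 at Day 104 (106 - 2). The Q2W visit tolerance is 3 days (Protocol 9.1.2) and the dose tolerance is 1 day (Table 2-2). Q2W doses fall on Days 1, 15, 29 and so on, so even weeks are dosing visits and odd weeks are not.

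**Where an early visit lands.** Three days early is Day 7n + 1 - 3 = 7n - 2. The previous week's window ends on Day 7(n - 1) + 1 + 4 = 7n - 2, the same day. Two days early is 7n - 1, the first day of the correct window. Three days late is 7n + 4, still inside it. Only a visit exactly 3 days early fails. A QW visit within 2 days never does.

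**Example.** Week 7 has target Day 50 and window 48-54. Seen on Day 47, it falls in the week 6 window (41-47, target 43). The week 6 dosing visit, held to Days 42-44, is at most 1 day from target; the Day 47 visit is 4 days away and is dropped. The week 8 dosing visit (Days 56-58) cannot fill the week 7 window, so week 7 is blank. If week 6 was missed, the Day 47 value is reported as week 6.

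**Non-dosing Q2W visits at target -3, through each table**

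| Table | Weeks that fail | Status |
|---|---|---|
| Vitals | 5, 7, 9, 11, 13, 15 | Clear |
| Chemistry/hematology | 5, 7 | Clear |
| PD | 7, 9, 11, 17 | Only if samples after week 5 may follow the visit window |

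- Vitals week 15 on Day 103 falls in week 14 (97-103).
- Vitals week 17 does not fail when the week 16 dose is on Day 113: its window opens on Day 117 = 120 - 3.
- PD week 17 on Day 117 falls in the row for Week 16, Day 116 (113 + 2 to 113 + 4 = 115-117).
- PD week 5 is excluded, because a sample 3 days early breaches the 12-hour limit in Table 2-1.
- Vitals from week 20 and chemistry from week 12 are not affected.

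**Expected blank weeks per Q2W subject.** The documents give no timing distribution, so two are assumed over -3 to +3 days: uniform, P(-3) = 1/7, and triangular with weights 1-2-3-4-3-2-1, P(-3) = 1/16.

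- Vitals: 6/7 = 0.86, or 6/16 = 0.38.
- Chemistry/hematology: 2/7 = 0.29, or 2/16 = 0.13.
- PD, if it applies: 4/7 = 0.57, or 4/16 = 0.25.

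**Chance that at least one of 6 subjects is blank at a given affected week,** 1 - (1 - p)^6: 11% for p = 0.02, 26% for p = 0.05, 32% for p = 1/16 and 60% for p = 1/7.

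**The case against.** The strongest case on the other side is that most weekly Q2W visits cannot compliantly be 3 days early and that little depends on the rest.

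- **Dosing visits.** A reader might infer that every weekly Q2W visit is exposed, such as vitals weeks 5-15 and 18. The documents do not support that. Even-week visits carry a dose that Table 2-2 limits to 1 day, or 2 days later on, and both fit inside the SAP window. This stands, and the count above is confined to odd weeks.
- **PD samples.** A reader might infer that Treg profiles are clearly hit. Table 2-1 holds these samples to 12 hours through week 5, and the matching Table 2-2 footnote is not visible. PD is therefore conditional.
- **Swapped points of the dosing interval.** A reader might infer routine confusion of mid-interval with pre-dose values. A compliant dosing visit is always nearer its target than the early odd-week visit, so it is kept. Wrong-week labelling needs a missed or non-compliant dosing visit. The usual result is a blank.
- **Consequence.** The SAP plans no statistical hypothesis. DLT and adverse event analyses do not use these windows, and maximum/minimum and worst-grade summaries are not organised by week. This stands and limits the weight of the point.

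None of this removes the mismatch for odd-week vitals and chemistry: nothing in either document exempts Q2W cohorts or keeps their scheduled label.

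**Conclusion.** The mismatch is exact. Appendix G moves a compliant Q2W non-dosing visit at target -3 into the previous week, where it is normally discarded. It holds clearly for six vitals weeks and two chemistry/hematology weeks, and conditionally for four PD weeks. QW cohorts lose nothing.

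The size depends on how often visits are exactly 3 days early. The 0.86 and 0.38 blank vitals weeks per subject assume the full tolerance is used and that dosing visits keep to their 1-day window. If sites rarely use the third day, the loss is smaller. The impact is modest and confined to descriptive by-visit summaries. The documents do not support reading it as a threat to the DLT, adverse event or worst-value results.

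Separately, the 3-day visit window in 9.1.2 and the 1-day dose window in Table 2-2 conflict at Q2W dosing visits and must be reconciled.

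**What to change.** **Preferred.** In Appendix G, map a scheduled visit that lies within its protocol visit window to its own scheduled week. Use day windows only for unscheduled, progressive disease, end-of-treatment and out-of-window visits.

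**Alternative.** Set the vitals and chemistry/hematology weekly rows after week 4 to target -3 to target +3, that is 7n - 2 to 7n + 4. The next row opens at 7(n + 1) - 2 = 7n + 5, so the rows stay contiguous, 7 days wide and without overlap. Move the bordering rows to match:

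- Vitals: week 4 ends on Day 32 and week 15 starts on Day 103.
- Chemistry/hematology: week 4 ends on Day 32 and week 8 starts on Day 54.

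If the PD rows are changed too, include week 17 and keep nominal labels for the Day 30/32 and Day 114/116 samples. State which sample window applies after week 5.

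**Cost.** SAP wording and one programming table, with no new data and no change to conduct. Under the alternative, a non-compliant visit 4 days late would be labelled with the next week.
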